7.7.2. COVID-19 case monitoring to detect imbalances across study groups (harm monitoring)

An unblinded statistician, who is not otherwise involved in the study, will monitor the number and severity of molecularly confirmed COVID-19 cases in the Ad26.COV2.S and placebo groups to identify an imbalance between groups if it occurs. The unblinded statistician will inform the DRC as soon as an imbalance between groups is detected.

As soon as 3 confirmed COVID-19 cases have occurred, and with every additional case, the unblinded statistician will tabulate the cases according to whether the participant received Ad26.COV2.S or placebo (i.e. active regimens will be pooled) and calculate the difference in proportions between the two groups (proportion in active – proportion in placebo). Two (two-sided) confidence intervals around this difference will be constructed, a 95% CI and an 80% CI (i.e. using z-values corresponding to alpha = 0.05 and alpha = 0.20), using Newcombe's method without continuity correction.

The Newcombe's confidence interval for a difference between proportions is calculated as follows:

$$\text{Lower limit: } (\hat{p}_1 - \hat{p}_2) - \sqrt{(\hat{p}_1 - L_1)^2 + (U_2 - \hat{p}_2)^2}$$

$$\text{Upper limit: } (\hat{p}_1 - \hat{p}_2) + \sqrt{(U_1 - \hat{p}_1)^2 + (\hat{p}_2 - L_2)^2}$$

Where L_i and U_i are the Wilson Lower and Upper confidence limits for p_i . The Wilson confidence limits without continuity correction for each binomial proportion $p_i = x_i/n_i$ ($i=1,2$) is given by:

$$\frac{1}{2(n_i + z^2)} \left((2n_i \hat{p}_i + z^2) \pm z \sqrt{4n_i \hat{p}_i (1 - \hat{p}_i) + z^2} \right)$$

If the upper limit of the two-sided 95% CI around the difference in proportions exceeds 0.10 (i.e. >10 percentage points difference between active and placebo), and the lower limit of the two-sided 80% CI around the difference in proportions exceeds 0 (i.e. >0 percentage points difference between active and placebo), then the unblinded statistician will conclude that there is an imbalance between active and placebo (where the proportion in active is greater than the proportion in placebo). Otherwise, the statistician will not conclude that there is an imbalance.

The same operations will be executed for severe COVID-19 cases, using these definitions of “severe” cases:

- COVID-19 cases requiring hospitalization,
- COVID-19 cases requiring hospitalization and the patient being admitted to the Intensive Care Unit,
- COVID-19 cases resulting in death (with death being at least probably related to COVID-19)

7.7.3. COVID-19-like Signs and Symptoms

If a participant experiences COVID-19-like symptoms (eg, cough, feverishness, dyspnea, gastrointestinal symptoms, anosmia), the following should take place:

- Participants should contact the study site at the time of symptom onset
- A nasal swab should be collected from the participant at home (using available material for home swabs) as soon as possible and preferably no longer than 2 to 3 days after the onset of symptoms and stored appropriately. It is preferred that the swab is taken by a caregiver (spouse, partner, relative, friend, or health care professional). If that is not possible, the participant can collect the swab him- or herself. The sample should be transferred to the study site by an appropriate method as soon as possible after being collected. A second nasal swab will be obtained 2 to 4 days after the first swab following the same procedures as the first nasal swab or at the study site if appropriate procedures are in place.

The presence of SARS-CoV-2 infection and influenza infection will be assessed at the study site by molecular testing using the nasal swab sample.

- Participants should complete the Symptoms of Infection with COVID-19 (SIC) and record their highest body temperature daily starting on the first day they experience symptoms. If either nasal swab is positive for SARS-CoV-2 or influenza, collection of data will continue until sign and symptom resolution. If the first nasal swab is negative, collection of data will continue until the negative test is confirmed by the second nasal swab.
- For participants with a positive test result for SARS-CoV 2 infection, a study visit will be conducted 28 days after symptom onset to assess the clinical course of the infection, record concomitant medications since symptom onset, and obtain a blood sample for evaluation of the immune response and other biomarkers.

The SIC asks participants to indicate, for each of 25 symptoms and on a daily basis, whether or not they experienced the symptom (Yes/No), and if Yes, to rate the severity (on an 11-point scale ranging from 0 to 10, where 0 = none to 10 = worst). In addition, 4 questions are asked that are asked to be responded to by Yes/No, without severity assessment.

The presence of SARS-CoV-2 infection and influenza infection will be assessed at the study site by molecular testing using the nasal swab sample.

The following analyses will be conducted at the time of the End of Study analysis or at an interim analysis^a:

The number and percentage of participants with at least one molecularly confirmed SARS-CoV-2 infection will be tabulated by vaccine regimen, for the entire study period only^b.

The analysis will be repeated pooling all active regimens vs. placebo, where data from all cohorts will be pooled. If at least 5 molecularly confirmed SARS-CoV-2 infection are observed, vaccine efficacy (VE) will be calculated with a 90% confidence interval (CI). Otherwise, no VE will be calculated and only the above mentioned descriptive statistical analysis will be conducted. The following paragraphs provide the rationale for only calculating VE when at least 5 events are observed, as well as the formula to calculate VE and its 90% CI.

Assuming a true VE of 70%, 23 events of molecularly confirmed SARS-CoV-2 infections are required to offer 80% power to detect vaccine efficacy exceeding zero ($H_0: VE = 0$) when using a one-sided alpha level of 0.05 (i.e. a 90% CI) and a randomization ratio of 4.65:1 (860 active:185 placebo). Assuming a true VE of 90%, 5 events are required to offer 80% power to detect vaccine efficacy exceeding zero ($H_0: VE = 0$) when using a one-sided alpha level of 0.05 (i.e. a 90% CI) and a randomization ratio of 4.65:1 (860 active:185 placebo).

^a All or some of the described analyses may also be performed prior to the End of Study analysis, but after the Primary analysis. Since no formal hypothesis tests are performed, no alpha spending will be applied.

^b Note that the observation period ends at the time of unblinding or receipt of an unscheduled vaccine, whichever occurs first, cf. section 9.7 of clinical trial protocol amendment 15. This censoring rule applies to all efficacy analyses.

The formula to calculate VE (as a percentage) is:

$$VE = 100 \times \left(1 - \frac{p}{r(1 - p)}\right)$$

Where p = proportion of events occurring among the group of participants vaccinated with Ad26.COV2.S, r = the ratio of the number participants vaccinated with Ad26.COV2.S to the number of participants vaccinated with placebo. 90% asymptotic Wald confidence limits will be calculated.

The number and percentage of participants with at least one molecularly confirmed Influenza infection will be tabulated by vaccine regimen, for the entire study period only.

The number and percentage of participants with at least one positive non-S protein ELISA (e.g., N ELISA), if available, will be tabulated by vaccine regimen. The analysis will be repeated pooling all active regimens vs. placebo, where data from all cohorts will be pooled. If at least 5 positive non-S protein ELISA events have been observed, VE can be calculated against this endpoint, using the same approach as outlined above for the VE against molecularly confirmed SARS-CoV-2 infection.

For each participant with confirmed COVID-19 infection, a narrative will be prepared based on the visit performed 28 days after the onset of COVID-19 signs and symptoms and other selected information from the clinical database, as available:

- participant ID
- vaccination regimen
- sex, race, ethnicity, age, BMI, dates at which vaccinations were received
- physical examination findings based on the visit performed 28 days after the onset of COVID-19 signs and symptoms
- vital signs including body temperature based on the visit performed 28 days after the onset of COVID-19 signs and symptoms
- concomitant medications since symptom onset
- Humoral immune responses as collected at the planned time points + those obtained from the blood sample taken on the visit performed 28 days after the onset of COVID-19 signs and symptoms. This information may be presented graphically.

For the analysis of the SIC (Patient Reported Outcomes, PRO) data, the following considerations apply

- An “episode” is defined as a period in which any symptoms are reported on the SIC, starting from the first day on which symptoms were reported until the first day that the PRO was not completed because the symptoms had resolved (this will be indicated in the SDTM data, with reason for not completing the PRO = “Symptoms resolved” (or similar) or death)
- A symptom (e.g. feeling generally unwell, fatigue, physical weakness, cough, etc.) is assumed to be present on each day the associated Yes/No question is answered “Yes” or the associated severity question has a rating > 0 .

- If the PRO was not completed due to the participant being too ill or due to the participant being hospitalized, the symptom will be considered present with severity score 10. If the PRO was not completed due to any other reason, no imputations will be done.

Duration of the episode will be calculated as episode end date – episode start date. Duration of each symptom will be calculated as last day of symptom reporting – first day of symptom reporting + 1. Duration of the maximum severity is defined as the last day of reporting the maximum severity – the first day of reporting the maximum severity + 1.

The following analyses will be conducted for confirmed SARS-CoV-2 infection cases and confirmed influenza infection cases separately:

- At the level of first episodes, the following statistics will be calculated: number of episodes, mean and median duration of episodes (with min, max, q1 and q3), and mean and median number of symptoms reported per episode (with min, max, q1 and q3).
- At the level of the symptoms for each first episode, the following statistics will be calculated: number of participants experiencing the symptom, mean and median duration of each symptom (with min, max, q1 and q3), median (with q1 and q3) of maximum severity of each symptom, median duration of the maximum severity of each symptom (with min, max, q1 and q3).
- At the level of the participants, for each episode and each symptom separately, the duration, and minimum and maximum severity scores will be tabulated (as available).

In addition, participant listings will be provided containing the SIC information for each time point.

More details about these analyses will be provided in the DPS.

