6. POPULATIONS FOR ANALYSIS

For vaccine studies, study intervention assignment will follow the as treated principle: all analyses (including safety, immunogenicity and efficacy analyses) will be analyzed by the actually received vaccine.

Population	Description
All screened participants (ALL)	The “all screened participants” set includes all participants that were screened, regardless of whether they were enrolled and/or randomized.
All randomized participants (ALL RANDOMIZED)	The “all randomized participants” set includes all participants that were randomized to one of the treatment groups.
Full Analyses Set (FAS)	The full analysis set will include all participants with at least one vaccine administration documented.
Per Protocol Immunogenicity Set (PPI)	The per protocol immunogenicity population will include all randomized and vaccinated participants for whom immunogenicity data are available excluding participants with major protocol deviations expecting to impact the immunogenicity outcomes. In addition, samples obtained after missed vaccinations or participants with natural infection occurring after screening (if applicable) will be excluded from the analysis set.
Per Protocol Efficacy Set (PPE)	The per protocol efficacy population will include all randomized participants having received at least 1 vaccination for whom efficacy data concerning endpoint measures are available. All efficacy analyses will be done according to the as treated principle (ie, actually received vaccinations).

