- “Post-Dose 1 and Post-Booster Doses Combined”, which refers to the complete regimen including all the booster doses in Cohort 2a. It includes the 28-day period after each vaccination (dose 1, booster dose 1, and booster dose 2).
- “Post-Dose 1, Post-Dose 2 and Post-Booster Doses Combined”, which refers to the complete regimen including all the booster doses in Cohort 2b. It includes the 28-day period after each vaccination (dose 1, dose 2, booster dose 1, and booster dose 2).

For some tables, e.g. SAE tables, a period “Entire study” will be defined. This will be a combination of all the active phases and periods, so that it covers the time window from vaccination 1 up to and including the end of the study (per participant).

The primary endpoint includes SAEs from the first vaccination until 6 months after completion of the primary regimen for cohorts 2a and 2b. This will be a combined period of post-dose 1 and post-dose 1 Follow Up (FU) (for Cohort 2a) and a combination of post-dose 1, post-dose 1 FU, post-dose 2, and post-dose 2 FU (for Cohort 2b). This period will be labeled “Entire Primary Regimen” or similar in the outputs.

The exploratory endpoints include SAEs from the first booster vaccination time point until the end of the regimen for Cohort 2. This will be a combined period of post-booster 1 until the last follow-up period in Cohorts 2a and 2b. This period will be labeled “Entire Booster Regimen” or similar in the outputs.

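### The only vaccine efficacy estimate runs over the entire study from the first injection, so it is diluted by cases arising before the vaccine can act; a companion estimate with a fixed lag should be added

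*SAP*

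**What the plan says.** Section 7.7.3 states that the number and percentage of "participants with at least one molecularly confirmed SARS-CoV-2 infection will be tabulated by vaccine regimen, for the entire study period", and the sentence restricts the tabulation to that period only. It continues: "The analysis will be repeated pooling all active regimens vs. placebo, where data from all cohorts will be pooled". VE with a 90% confidence interval is calculated from that pooled comparison once at least 5 infections have been observed.

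Section 7.1.2 defines the entire-study period "so that it covers the time window from vaccination 1 up to and including the end of the study (per participant"). The one rule in 7.7.3 that modifies this window is footnote b, under which "the observation period ends at the time of unblinding or receipt of an unscheduled vaccine, whichever occurs first". It limits the end of the window and leaves the start at the first injection.

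The Per Protocol Efficacy set in section 6 consists of "all randomized participants having received at least 1 vaccination for whom efficacy data concerning endpoint measures are available". It contains no condition on when a case began. Section 7.1.1 would allow efficacy results by phase where appropriate, but 7.7.3 narrows this to the whole study.

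The 5-event threshold is justified by power: "Assuming a true VE of 90%, 5 events are required to offer 80% power to detect vaccine efficacy exceeding zero", with a companion figure of 23 events at a true VE of 70%. Both use a one-sided alpha of 0.05 and an 860:185 allocation.

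**The concern.** A participant whose symptoms begin a few days after dose 1 was probably infected around the time of vaccination or before an immune response could form. Such a case says little about whether the vaccine works, yet it counts in the numerator and toward the threshold. If the vaccine has no effect in that window, these cases split between the arms by allocation alone: 860/1045 = 82% are expected in the active group. Mixing them with later cases moves VE toward zero.

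The power rationale makes no allowance for this. It applies the full 70% or 90% to every counted case, which fits a window opening at dose 1 only if protection is immediate. The SAP itself models immune responses at 28 days after dose 1 (section 7.7.1.7).

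At the smallest permitted event count, single cases matter, and footnote a to 7.7.3 lets the analysis be done before the End of Study analysis. A low VE could then reflect the counting window rather than the vaccine, and the plan provides no second estimate to tell the two apart.

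**Working it through.** **Inputs from the SAP (7.7.3).** Allocation 860:185, so r = 860/185 = 4.649. One-sided alpha 0.05. Stated 80% power at 23 events for VE 70% and at 5 events for VE 90%.

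**Assumptions, not in the SAP.** Constant incidence over T days of observation; no vaccine effect in days 1-14; VE 90% afterwards; T = 60, 90, 180 or 365 days.

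**Step 1: reproduce the stated event counts.** Condition on the total number of events and use the exact binomial for the number in the active group.

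- With no effect, the active share is p0 = r/(1+r) = 0.823.
- With efficacy VE, it is p1 = r(1-VE)/[1+r(1-VE)], which is 0.582 at 70% and 0.317 at 90%.
- 23 events: reject at 15 or fewer active cases; alpha 0.038; power 81.2%.
- 5 events: reject at 2 or fewer active cases; alpha 0.042; power 81.3%.

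The SAP's 23 and 5 are therefore correct on their own terms.

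**Step 2: dilution.** Let w = 14/T be the share of observation time before protection. Then RR = w × 1 + (1-w) × 0.10, and entire-study VE = 1 - RR. Power is the probability of 2 or fewer active cases out of 5 at the diluted VE.

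**Step 3: share of all counted events that fall in days 1-14.** Per placebo participant, early events are proportional to w(1+r) and later ones to (1-w)(1+0.1r). The share is w(1+r) / [w(1+r) + (1-w)(1+0.1r)], with 1+r = 5.649 and 1+0.1r = 1.465.

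| T (days) | w | RR | Entire-study VE | Power at 5 events | Early share of events |
|---|---|---|---|---|---|
| 365 | 0.038 | 0.135 | 86.5% | 71% | 13% |
| 180 | 0.078 | 0.170 | 83% | 61% | 25% |
| 90 | 0.156 | 0.240 | 76% | 45% | 42% |
| 60 | 0.233 | 0.310 | 69% | 33% | 54% |

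For T = 180: early 0.0778 × 5.649 = 0.439; later 0.922 × 1.465 = 1.351; share 0.439/1.790 = 25%.

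**Step 4: sensitivity at small counts.** With x active and y placebo cases, the SAP's formula reduces to VE = 1 - x/(r·y).

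- 2 active, 3 placebo: VE 86%, exact one-sided p = 0.042.
- One further early active case (3:3): VE 78%, p = 0.073.
- Two further (4:3): VE 71%, p = 0.11.

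**The case against.** The strongest reply is that the planned analysis does what its endpoint asks. Section 7.5 defines the exploratory efficacy endpoint as confirmed cases in vaccine versus placebo recipients over the overall study. An all-cases VE from first vaccination is a legitimate estimate of that quantity, and it keeps everyone randomized and vaccinated. VE is exploratory, footnote a to 7.7.3 says no formal hypothesis test is made, and the bias is conservative. Early cases are also visible, since each confirmed case gets a narrative with vaccination dates. All of this stands. A reader might infer that the entire-study VE is wrong and should be demoted or replaced; the document does not support that.

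Size is the second reply. Planned follow-up is long: SAEs to 1 year after the second vaccination in Cohorts 1 and 3 (section 7.3), and target visits at Day 731 and Day 787 in Cohort 2 (changes to previous versions). At 365 days the loss is only 3.5 points. A reader might infer from the shortest scenario that 23 events are needed instead of 5. That fits only the 60-day case, where VE falls to 69%. Footnote b can shorten observation, but the SAP does not say by how much.

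Third, the SAP contains no 14-day figure, and the pooled analysis mixes one-dose and two-dose regimens, so any single lag from dose 1 is a convention. Excluding 13% to 54% of events is also a real cost, and a lagged VE gated on 5 lagged events might often go uncalculated. That supports adding the lagged estimate beside the planned one.

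None of these replies supplies a start rule for case counting, or a second estimate to set beside the diluted one.

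**Conclusion.** The concern holds in a limited form. Section 7.7.3 allows VE only from the first injection, so cases the vaccine could not have prevented are counted and dilute the estimate toward zero. The power rationale does not allow for them, although its event counts reproduce.

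The extent cannot be fixed from the SAP. Under the stated assumptions, a true later VE of 90% appears as about 87% with a year of observation and as 69% to 83% with 60 to 180 days, and power at 5 events drops from 81% to between 71% and 33%. Different incidence over time or some early protection would change these figures. Because VE is exploratory and untested, what is affected is how the estimate is read; no confirmatory conclusion depends on it. The gap is the absence of a pre-specified second estimate, which makes this a cheap improvement.

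**What to change.** Keep the entire-study VE as planned. Add to 7.7.3 a companion VE for the pooled active-versus-placebo analysis of molecularly confirmed SARS-CoV-2 infection, specified as follows.

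- Count only first confirmed cases with symptom onset at or after a stated lag from first vaccination.
- Fix the lag before any unblinded efficacy data are examined. Fourteen days is one possible choice and should be labelled as an assumption.
- Take r from participants still under observation and uninfected at the lag. The end-of-observation rule in footnote b is unchanged.
- If fewer than 5 lagged events occur, report the counts descriptively without a VE.

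The data needed are already collected: symptoms are recorded daily from onset, and vaccination dates are held for the case narratives. The effort is a short addition to the SAP and a date filter. The price is fewer events and a wider interval, with about 13% of events excluded at 365 days, 25% at 180 and 42% at 90 under the assumptions above. The rule does not carry over to the non-S protein ELISA endpoint, which has no onset date, so the text should limit the companion analysis to molecularly confirmed infection.

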7.1.5. Analyses by Cohort and Pooled Across Cohorts

All analyses are planned to be performed within each cohort separately, unless explicitly indicated that data will be pooled across cohorts.

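### The pooled vaccine efficacy uses one crude ratio over all cohorts, so it may be biased if both allocation ratio and infection risk differ by cohort; stratifying by cohort is a cheap safeguard

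*SAP*

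**What the plan says.** SAP section 7.1.5 makes analysis by cohort the default: "All analyses are planned to be performed within each cohort separately, unless explicitly indicated that data will be pooled across cohorts". Section 7.7.3 uses that exception for VE, setting all active regimens against placebo, "where data from all cohorts will be pooled".

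VE is then 100 × (1 − p / (r(1 − p))). Here p is the active share of all events, and "r = the ratio of the number participants vaccinated with Ad26.COV2.S to the number of participants vaccinated with placebo". The interval is a 90% Wald interval. The formula has no term for cohort or for person-time. Later in section 7.7.3 the same approach is carried over to VE against a positive non-S protein ELISA.

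The only allocation figure in the SAP is the overall one, "a randomization ratio of 4.65:1 (860 active:185 placebo". Section 7.1.2 names five cohorts (1a, 1b, 2a, 2b and 3), which differ in number of doses and in boosters. The trial covers adults aged 18 to 55 and adults aged 65 and older.

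**The concern.** Randomisation protects the placebo comparison within the groups in which participants were allocated. When cohorts are collapsed, the crude ratio keeps that protection if the active:placebo ratio is the same in every cohort, or if infection risk is. If both differ, a high-ratio cohort supplies a different share of the active group than of the placebo group, and its infection risk is mixed into the comparison. VE is understated if the high-ratio cohorts carry the higher risk and overstated if they carry the lower. A vaccine with no effect could show a non-zero VE.

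Different follow-up by cohort acts in the same way. A footnote to section 7.7.3 ends each participant's observation at unblinding or at an unscheduled vaccine, so follow-up need not be equal across cohorts.

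The SAP takes more care elsewhere. When section 7.7.1.7 pools immunogenicity data over cohorts, the models include age, number of doses and dose level. The pooled VE adjusts for nothing.

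**Working it through.** **1. The plan's own figures.** With r = 860/185 = 4.649, the number of active cases among n cases is binomial with p = r(1 − VE) / (1 + r(1 − VE)). This gives p = 0.8230 at VE 0%, 0.5824 at VE 70% and 0.3173 at VE 90%.
- "Assuming a true VE of 70%, 23 events of molecularly confirmed SARS-CoV-2 infections are required to offer 80% power": with n = 23, reject at 15 or fewer active cases; one-sided alpha 0.0382, power 0.812.
- "Assuming a true VE of 90%, 5 events are required to offer 80% power": with n = 5, reject at 2 or fewer active cases; alpha 0.0418, power 0.813.

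Both statements reproduce and are not in question.

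**2. What 860:185 implies.** 860/5 = 172 and 185/5 = 37, so the ratio in lowest terms is 172:37. For all five cohorts to share it exactly, each would need exactly 172 + 37 = 209 participants. That is unlikely, so a mix of ratios is the natural reading. It remains an inference, and it does not show how far apart the ratios are.

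**3. Size of the bias (assumed inputs).** Take two blocks allocated 4:1 and k:1 with a and b placebo participants, where a + b = 185 and 4a + kb = 860. Placebo risks are 2% in one block and 6% in the other, and true VE is the same in both.

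Example, k = 8: b = (860 − 740)/4 = 30 and a = 155, so the blocks are 620:155 and 240:30. Put the 6% risk in the 8:1 block and set true VE to 70%.
- Active events: 0.3 × (620 × 0.02 + 240 × 0.06) = 8.04.
- Placebo events: 155 × 0.02 + 30 × 0.06 = 4.90.
- Crude VE: 1 − (8.04/4.90)/4.649 = 64.7%.

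| Blocks | True 70%, k:1 block at 6% | True 70%, k:1 block at 2% | True 0%, k:1 block at 6% | True 0%, k:1 block at 2% |
|---|---|---|---|---|
| 4:1 with 5:1 (260:65, 600:120) | 68.7% | 71.7% | −4.3% | +5.8% |
| 4:1 with 6:1 (500:125, 360:60) | 66.6% | 72.4% | −11.4% | +8.0% |
| 4:1 with 8:1 (620:155, 240:30) | 64.7% | 72.6% | −17.7% | +8.7% |
| 4:1 with 10:1 (660:165, 200:20) | 63.9% | 72.7% | −20.5% | +8.9% |
| 4:1 with 12:1 (680:170, 180:15) | 63.4% | 72.7% | −22.1% | +9.0% |

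If the two risks are equal, the crude formula returns the true VE whatever the ratios. If the ratios are equal, it does so whatever the risks.

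**4. The stratified estimate.** In the k = 8 example, expected active events by block are 3.72 and 4.32, and expected placebo events are 3.10 and 1.80. The Mantel-Haenszel relative risk is (3.72 × 155/775 + 4.32 × 30/270) / (3.10 × 620/775 + 1.80 × 240/270) = 1.224/4.080 = 0.300, so VE = 70.0%. It returns the true value in every row of the table.

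**5. Comparison with sampling error.** At 23 events and VE 70%, expected cases are 13.4 active and 9.6 placebo. Taking the Wald interval on the log scale (the SAP does not name the scale), SE = √(1/13.4 + 1/9.6) = 0.423. The 90% limits for VE are 1 − 0.3 × exp(±1.645 × 0.423), about 40% to 85%.

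**The case against.** The strongest reply is that the premise cannot be shown from the document. A reader might infer that 4.65:1 proves different cohort ratios and that the VE is therefore confounded. The SAP supports neither step. An odd overall ratio makes mixed ratios likely, no more, and unequal ratios alone do not bias the crude VE. Risk or follow-up must differ by cohort too, and no attack rate is given. That stands.

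Size is the second reply. The mildest natural pair, 4:1 with 5:1, moves a true 70% by less than 2 points. In a simulation of the 620:155 plus 240:30 split with a threefold risk gap and 8 to 23 expected events, the crude 90% log-scale interval covered the truth 90% to 96% of the time. Root mean squared error on the log relative risk was similar for crude and Mantel-Haenszel: 0.51 against 0.48 in one case, and 0.63 against 0.69 in another, where crude did better. This also stands as to size. Still, the bias does not shrink as events accrue, and the interval does not reflect it.

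Third, VE is an exploratory endpoint with no formal test, and infections are also tabulated by regimen, so an imbalance between cohorts could be noticed. That lowers the priority, but a table does not correct the pooled estimate. Finally, section 7.7.3 does not contradict section 7.1.5, which allows explicit pooling. That is accepted and no contradiction is claimed.

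**Conclusion.** The point holds as a caution about a stated method. The SAP fixes an unstratified pooled VE that may be biased, in a direction that cannot be known from the document, if both the allocation ratio and the infection risk or follow-up differ by cohort.

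Under the assumed two-block splits with a threefold risk gap, the error at a true VE of 70% is between 6.6 points too low and 2.7 points too high. At a true VE of 0% the estimate lies between −22.1% and +9.0%. These figures rest on assumed ratios and risks, and the actual values may be milder. The effect is small next to the planned interval, and the analysis is exploratory. This is a worthwhile improvement, not a flaw that threatens a conclusion of the trial.

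**What to change.** In section 7.7.3, define the pooled VE as 1 minus the Mantel-Haenszel relative risk stratified by cohort, with a stratified 90% interval, and use an exact conditional stratified version when events are few. Keep the crude VE as a supportive figure. Apply the same rule to VE against a positive non-S protein ELISA.

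The cost is a sentence or two in the SAP, since cohort is already in the data. Strata without events contribute nothing, and the interval may be slightly wider. Stratifying head counts does not correct for follow-up that differs between arms within a cohort; that would need person-time, for example a Poisson model with cohort and a follow-up offset.
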